1.0 BACKGROUND AND RATIONALE

1.1 Pediatric Brain Tumors

Pediatric brain tumors comprise a heterogeneous group of tumors, including gliomas (high and low grade), medulloblastoma, ependymoma, primitive neuroectodermal tumor (PNET), atypical teratoid/rhabdoid tumor (ATRT), choroid plexus carcinoma, as well as other rarer tumors. Gliomas are the most common tumors in pediatrics, especially grade I (pilocytic astrocytoma) and grade II. High grade gliomas include anaplastic astrocytoma, glioblastoma (GBM), and mixed oligoastrocytomas. As with adults, high grade gliomas in pediatrics confer a poor prognosis. The current standard chemoradiotherapy for newly diagnosed high grade glioma produces only a modest survival benefit in pediatric patients, with less than 20% alive at five years [1]. All recurrent pediatric malignant tumors have a very poor prognosis with no standard and few effective therapeutic options available. Most children with relapsed disease will succumb within 3 years of recurrence with any malignant tumors. One of the challenges in treating brain tumors is the limitation of many agents to penetrate the blood brain barrier (BBB). Several methods to overcome BBB disruption have been attempted and currently undergoing studies, including intra-arterial chemotherapy administration, direct intratumoral/intracavitary placement of chemotherapy agents, and convection-enhanced delivery of agents, although a method with clear survival benefit has yet to be demonstrated [2].

1.2 Penetrating the Blood Brain Barrier (BBB)

[figure not shown]
Despite the fact that several cytotoxic and targeted agents have shown significant anti-growth activity in cultured cells, when tested in clinical trials there has been with minimal success, particularly in high grade glioma patients [3, 4]. In one study of pediatric high grade glioma using primary tumor cell cultures, it was shown that several classic chemotherapy agents, including anthracyclines, have a high cytotoxicity in vitro [4]. The high failure rate is in part due to the redundancy in key growth pathways and in drug resistance of malignant cells. Another explanation is the poor CNS penetration many of these drugs have due to the blood brain barrier (BBB). As a result, high doses of drugs were used in studies to achieve therapeutic drug concentrations in the CNS, which led to significant systemic toxicities and limited their clinical usefulness [5]. Preclinical models have shown that the delivery across the blood brain barrier depends on the size and molecular weight of the compound, even after blood brain disruption by mannitol [6]. Thus, an outstanding challenge in neuro-oncology has been to generate drugs that have excellent CNS penetration or methods that can compromise the BBB to enhance drug delivery.

The impact of the BBB on primary brain tumors has been most studied in GBM. GBM typically appear on MR imaging as rim-enhancing masses, suggesting that the BBB within the growth-intensive rim is impaired because contrast enhancement reflects increased BBB permeability [7, 8]. Consequently, delivery of cytotoxic agents to the tumor rim is higher than that to normal brain tissue. However, beyond the enhancing rim – the peritumoral

region – where most micrometastatic GBM cells reside, the BBB remains relatively intact as demonstrated by the lack of contrast enhancement. As a result, access of cytotoxic drugs to this region is predicted to be more limited. Similar findings have also been observed in brain metastases arising from extracranial tumors. In many cancers, responses of brain metastases to systemic chemotherapy tend to closely parallel those of extra-cranial tumors [9-14]. Yet brain metastasis still represents a significantly poorer prognostic indicator than extracranial metastasis. This is likely because of the inherent nature of brain metastatic foci compromising critical neurological functions. Another possible explanation for this apparent paradox is that although cytotoxic agents can readily access brain metastases (BBB disrupted), they fail to reach therapeutic levels in the peritumoral or distant foci of brain micrometastases (BBB intact). Evidence supporting this theory came from studies in which drug levels of several cytotoxic agents were sampled in tumors and the surrounding normal brain tissue at the time of surgery or autopsy. Drug concentrations were at the highest in the tumors, and then rapidly decreased up to 40 fold lower within 2 cm distance from the viable tumor edge [15-17]. Evidence also suggests that efflux transporters in the endothelial cells of the BBB, such as multi drug resistance gene (MDR1) and multi drug resistance-related protein gene (MRP1), prevent agents from crossing the BBB [4, 18], and expression of these proteins negatively correlates with achieved concentration of chemotherapy within tumor cells [18]. Overall, these results support two notions: 1) the BBB and its integrity negatively correlate with delivery and therapeutic effect of cytotoxic agents; and 2) if we can disrupt the BBB in the peritumoral region, we could improve cytotoxic chemotherapy delivery in this area. In GBM, most recurrent tumors arise within the peritumoral region – in one series, 90% of GBM relapses occurred within 2-3 cm margin of the primary site [19] - therefore elimination of micrometastatic GBM cells in this area will likely improve long-term disease control.

To circumvent the BBB problem in local drug delivery, recent approaches have focused on bypassing it. A common method is the use of Gliadel wafers, a polymer implant impregnated with the chemotherapeutic agent BCNU and placed intraoperatively in the resection cavity to evade the BBB. This approach resulted in a statistically significant but modest survival advantage in both newly diagnosed and recurrent GBM [20-22]. The modest benefit of Gliadel could be due to the short duration of drug delivery – most BCNU is released over a period of 5 days[23]. However, the fact that direct delivery of a cytotoxic drug into the resection cavity for as little as 5 days could improve survival of GBM patients to a degree approaching that achieved by 8 months of systemic temozolomide chemotherapy is remarkable in itself, supporting the theory that the BBB is critical to cytotoxic chemotherapy effect. Unfortunately, Gliadel is not widely utilized as it requires a major surgery and can impair wound healing. Another approach of bypassing the BBB is the convection enhanced delivery system, in which a catheter is surgically inserted into the tumor to deliver chemotherapy [24]. This invasive procedure requires prolonged hospitalization, meticulous maintenance of the external catheter to prevent serious complications, and as a result remains investigational and is rarely used.

1.3 MRI-guided Laser Ablation (MLA)

[figure not shown]

MLA is a minimally invasive laser surgery currently FDA approved for cytoreductive treatment of brain tumors, both primary and metastatic [25]. [name] at Washington University performed one of the first MLA procedures in the country and is an international expert in laser ablation treatment of brain tumors. Currently Washington University has one of the largest clinical experiences using this new technology (Monteris, Winnipeg, CA). MLA employs a small incision in the scalp and skull, through which a thin laser probe is inserted and guided by MR imaging to the core of a tumor mass where it delivers hyperthermic ablation from the core to the rim. The maximal temperature in the core can reach greater than 70°C

resulting in coagulative necrosis (Fig. 1). The temperature decreases in the peritumoral region but remains high enough (>40°C) to induce changes in the BBB as evidenced by new peritumoral contrast enhancement extending several centimeters from the tumor edge, while the original tumor enhancement is lost due to the heat ablation (Figs. 1 & 2). These observations suggest that an interesting side effect of MLA is the disruption of the peritumoral BBB. These changes often persist for several weeks (not shown), providing a rare window of opportunity during which drug delivery can be enhanced to eliminate infiltrative tumor cells residing in this region where most recurrences occur.

Whether MLA indeed causes BBB disruption remains unexplored and is the main focus of this study. Interestingly, the role of hyperthermia in inducing increased BBB permeability has been previously described in several animal models. In a rodent model of human glioma, the global heating of a mouse's head to 42°C for 30 minutes in a warm water bath

significantly increased the maximal brain concentration of a thermosensitive liposome encapsulated with the chemotherapeutic drug Adriamycin [26]. To effect locoregional hyperthermia in the brain, retrograde infusion of a hyperthermic saline solution at 43°C into the left external carotid artery in the Wistar rat model reversibly increased BBB permeability to Evans-blue albumin in the left cerebral hemisphere[27]. In the most analogous method to the MLA, Nd:YAG laser-induced thermo-therapy to the left forebrain of Fischer rats resulted in locoregional disruption of the BBB as evidenced by increased locoregional passage of the Evans blue dye, serum proteins (e.g. fibrinogen and IgM), and the cytotoxic drug paclitaxel [28].

Based on these results, we hypothesize that hyperthermia-induced disruption of the peritumoral BBB by MLA (Fig. 2) represents a potentially powerful tool to enhance delivery of chemotherapy to this region to effectively target residual disease in addition to maximal cytoreduction of the tumor.

1.3.1 Prior Clinical Experience with MLA

We have had one of the largest clinical experiences using MLA in the country. To date we have done more than 80 cases, of which approximately two-thirds are high-grade glial neoplasms. In regards to adverse events, patients have experienced transient aphasia, transient hemiparesis, transient hyponatremia, and a documented case of lower extremity deep venous thrombosis. Patients with aphasia or hemiparesis improved over time with steroid therapy. Hyponatremia resolved spontaneously. One patient experienced fatal meningitis. Subsequent in-depth analysis revealed that this patient's meningitis was due to an operating room infrastructure-related contamination and not due to equipment contamination related to performance of the MLA procedure.

1.4 MLA followed by Standard of Care in Newly Diagnosed Glioma Patients (Arm A)

MLA offers an alternative to some patients with tumors that are unresectable. Complete surgical resection of grade I and II gliomas have a >90% overall survival, although complete resection is not always possible due to the location of the tumor. For tumors with less than a complete resection, chemotherapy or radiation therapy is offered for progressive

and/or symptomatic tumors. For high grade gliomas, patients who have a complete resection of the enhancing tumor at time of diagnosis [29, 30] or at relapse have a longer survival compared to those with residual disease [31]. In this arm of the study, patients with any grade glioma who are candidates for MLA will undergo this procedure followed by standard of care treatment.

1.5 MLA followed by Doxorubicin and Etoposide in Relapsed Malignant Tumor Patients (Arm B)

The ideal cytotoxic drugs for the purpose of this proposal should have potent activities against malignant cell lines *in vitro*, and *in vivo* activity that is limited by blood brain barrier function. Doxorubicin has been shown to kill a large number of high grade glioma cell lines *in vitro* [18, 32]. However, it has poor CNS penetration and has not been used extensively in CNS tumors. Doxorubicin and other anthracyclines induce cytotoxicity through intercalating between DNA base pairs, thereby interfering with strand elongation by DNA and RNA polymerase. Doxorubicin also affects topoisomerase II, which creates temporary double-strand DNA breaks during DNA replication. Doxorubicin stabilizes the DNA-topoII complex leading to double-strand DNA breaks and cell death. Doxorubicin has a wide volume of distribution with tissue levels proportional to the DNA content of the tissue. Doxorubicin is 75% bound to plasma proteins. Doxorubicin is mostly metabolized in the liver and eliminated mainly as glucuronide or hydroxylated conjugates in the bile and feces. The half-life of doxorubicin is 1 to 3 hours.

Maintenance chemotherapy using low-dose etoposide (21-day cycles) will be given following the course of doxorubicin. Low-dose etoposide has been found effective in treating relapsed brain tumor patients by extending PFS [33-36]. Etoposide is a topoisomerase II inhibitor and has been shown to inhibit tumor cell proliferation at high doses and to function as an anti-angiogenic agent when administered in low daily doses (metronomic chemotherapy) [37]. *In vitro* and pre-clinical studies demonstrate that low dose daily etoposide inhibits secretion of angiogenic factors, proliferation of endothelial cells, and endothelial tube formation [37]. This agent has been well tolerated in pediatric patients when given as low-dose, metronomic therapy.

In this arm, we are testing the concept that increased delivery of cytotoxic chemotherapy to the peritumoral region after MLA will result in increased peritumoral disease control. Although this approach appears to be similar to the dose escalation method, one clear difference is that in the dose escalation method, increasing systemic doses of drugs are used to achieve adequate drug concentrations in the CNS at the expense of significant systemic and global CNS toxicities, especially at doses near or exceeding the maximal tolerated dose. Therefore, the lack of benefits at high systemic doses may in part be due to excessive toxicities. On the other hand, in the MLA-enhanced drug delivery system, lower doses of drugs will be given more frequently to limit systemic toxicities and to selectively concentrate drugs in the peritumoral region where therapeutic action is desired, thus also reducing CNS toxicities.

In pediatric malignancies, doxorubicin is well tolerated and is given in combination with

other cytotoxic drugs. In high risk acute lymphoblastic leukemia, doxorubicin is given at 25 mg/m² IV weekly for 4 weeks in combination with vincristine. In Ewing's sarcoma, doxorubicin is given at 75 mg/m² IV in combination with vincristine and cyclophosphamide, alternating with ifosfamide and etoposide every 2 weeks. Similar dosing and schedules are given in other solid tumors, such as neuroblastoma and osteosarcoma. In ATRT, doxorubicin at 60 mg/m² (over 2 days) 2-3 weeks apart in combination with multiple other cytotoxic agents [38]. We expect doxorubicin 25 mg/m²/dose weekly for 6 weeks to be well tolerated. This is to minimize systemic toxicity while still achieving adequate drug delivery in the peritumoral region if the BBB is disrupted and to give continuous treatment during the window of MLA-induced peritumoral BBB disruption (6 weeks).

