2.0 OBJECTIVES

2.1 Primary Objectives

1. To determine progression-free survival (PFS) and overall survival (OS) of patients with new diagnosis glioma who are candidates for MLA (Arm A).
2. To determine 6-month progression-free survival (6PFS) in patients who receive doxorubicin immediately following MLA and low-dose etoposide as maintenance therapy in patients who are candidates for MLA with any type relapsed malignant brain tumors (Arm B).
3. To evaluate quality of life (QOL) using Karnofsky or Lansky performance status in patients following MLA and in patients who receive doxorubicin and maintenance etoposide after MLA.

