5.1.2 Arm B

Six patients enrolled to this study will be in Arm B; patients may be enrolled to Arm B at any time throughout the lifetime of the study. Arm B patients will undergo MLA and will begin doxorubicin (as described in Section 5.4) within approximately 7 days following MLA (range 2-14 days)

Arm B patients will undergo DSC and DCE-MRI at the following time points along with standard of care imaging:

- no more than 3 weeks prior to MLA (OPTIONAL)
- within approximately 4 days after MLA
- 2-4 weeks after MLA
- every 8 weeks (+/- 7 days) until 2 years have elapsed or disease progression (see Section 9.1), whichever comes first

Arm B patients will have 7 mL blood drawn at the following time points:

- before MLA; this sample can be collected any time during the 3 days before or the day of the procedure until the start of the procedure
- within approximately 3 days after MLA
- weekly (+/- 3 days) before (on the same day as) chemotherapy for the 6 weeks post-MLA
- every 8 weeks (+/- 7 days) at time points correlating with MRIs for the first 2 years or until disease progression, whichever comes first

The purpose of these blood draws is to measure serum levels of brain-specific factors (S100B, GFAP, and BSE) and cytokine levels. PBMC (for the pre- and post-MLA samples) will also be isolated to determine the phenotypes and functions of peripheral blood immune cells following MLA (see Section 9.2 -9.4). This is in addition to blood samples for routine laboratory prior to chemotherapy and surgery. During the weeks of DSC/DCE-MRI, biomarker lab must be drawn on the same day as DSC/DCE-MRI (prior to the scan).

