10.0 STUDY CALENDAR

10.1 Arm A Study Calendar

	Baseline ¹	MLA	3 Days Post-MLA	2-4 Weeks Post-MLA	Every 12 Wks Thereafter for 12 months Post-MLA ⁴	F/U ¹⁰
Informed consent	X					
Medical history	X					
Physical exam incl. wt	X		X ³	X	X ⁹	X ¹¹
Karnofsky/Lansky	X		X	X	X ⁹	X ¹¹
CBC	X					
CMP	X					
Urine or serum β HCG	X ⁷					
MRI with DCE/DSC	X ⁸		X ²	X ²	X ⁹	X ¹¹
Biopsy		X ⁸				
Blood to measure brain-specific factors (Sections 9.2-9.4)	X		X ²	X ²	X ⁹	X ¹¹
Adverse event assessment ⁵		X	X	X	X	X

1. No more than 21 days prior to MLA.

2. +/- 3 days

3. Weight not required

4. Patients will be followed every 12 weeks from the Week 4 MRI until 1 year has elapsed since MLA or progression, whichever occurs first. After progression, vital status and subsequent treatment will be recorded.

5. Through one year or off protocol.

6. To be obtained with MRI.

7. Females of childbearing potential

8. Optional

9. +/- 7 days

10. F/U every 6 months or at event occurrence for 5 years or until death, whichever occurs first

11. +/- 2 weeks

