10.2 Arm B Study Calendar

	B/L ¹	MLA	3 Days Post-MLA	Wk 1 ⁴	Wk 2 ⁴	Wk 3 ⁴	Wk 4 ⁴	Wk 5 ⁴	Wk 6 ⁴	Monthly ⁵	F/U ¹⁰
Informed consent	X										
Medical history	X									X	
Physical exam incl. wt	X			X	X	X	X	X	X	X	X ¹⁵
Karnofsky/Lansky	X			X	X	X	X	X	X	X	X ¹⁵
CBC	X			X	X	X	X	X	X	X	
CMP	X			X			X			X	
Urine or serum β HCG	X ¹²										
Echocardiogram	X ²										
MRI with DCE/DSC	X ¹⁴		X		X ¹¹					X ^{5,6}	
Biopsy		X ¹⁴									
Blood to measure brain-specific factors (Section 9.2-9.4)		X ³	X	X ⁷	X ⁷	X ⁷	X ⁷	X ⁷	X ⁷	X ^{5,6}	
Doxorubicin ⁸				X	X	X	X	X	X		
Etoposide ¹³										X	
AE assessment ⁹		X	-----								X

1. No more than 21 days prior to MLA.

2. No more than 1 year prior to registration.

3. May be collected any time during the 3 days before or the day of the procedure until the start of the procedure.

4. +/- 3 days

5. +/- 7 days

6. Every 8 weeks for the first 2 years or until disease progression, whichever occurs first. To coincide with MRI. After progression, vital status and subsequent treatment will be recorded.

7. Same day as chemotherapy.

8. To begin approximately 7 days after MLA.

9. Through one year or off protocol

10. Patients will be followed every 6 months or at event occurrence for 5 years or until death, whichever occurs first.

11. To be obtained 2-4 weeks post-MLA

12. Females of childbearing potential

13. To be started at time of count recovery after the 6 weeks of treatment with doxorubicin has concluded.

14. Optional

15. +/- 2 weeks

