PFS and OS will be estimated by Kaplan-Meier product limit method. The progression-free survival and overall survival probabilities at certain time points (e.g. 3 months, 6 months) will be presented as well. The difference in OS between Arm A and the historical control of bevacizumab alone will be compared by log-rank test. The quality of life (QOL) using Karnofsky or Lansky performance status will be characterized by summary statistics (mean, standard deviation and range).

The tumor-specific immune responses are collected at pre and post-MLA treatment. Paired t-test will be used to determine the effects of MLA treatment on patient's tumor-specific immune responses. Cox proportional hazard model will be used to determine the relationship between the duration of MLA-induced BBB disruption and PFS.

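### After the same laser ablation, low-grade procedure-related events must be reported in Arm A but not in Arm B, and only Arm A has a clinical assessment marked at 3 days

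*Combined protocol and SAP*

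**What the plan says.** Section 1.3.1 lists the effects seen so far after MLA: "patients have experienced transient aphasia, transient hemiparesis, transient hyponatremia, and a documented case of lower extremity deep venous thrombosis". On their course it says "Patients with aphasia or hemiparesis improved over time with steroid therapy". It gives no counts, onset times or durations.

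Section 7.7 sets two reporting rules. Arm A reports events of any grade judged at least possibly related to the MLA, tracked for 30 days after the procedure. Arm B reports events of grade 3 or worse irrespective of cause, tracked until 30 days after the last study treatment. Nothing in 7.7 makes a lower-grade MLA-related event reportable in Arm B.

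The calendars also differ. In 10.1 (Arm A) the 3-day column marks a physical exam, footnoted "Weight not required", and Karnofsky/Lansky. In 10.2 (Arm B) the same column marks MRI and blood and leaves those two rows blank. They are next marked at Week 1, together with the first doxorubicin dose, and then every week to Week 6. Doxorubicin is footnoted "To begin approximately 7 days after MLA"; Section 5.1.2 has it start "within approximately 7 days following MLA (range 2-14 days".

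Primary objective 3 in Section 2.1 is "To evaluate quality of life (QOL) using Karnofsky or Lansky performance status in patients following MLA", and also in patients given chemotherapy after MLA. Section 13.0 asks for a toxicity summary by arm.

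**The concern.** The procedure is the same in both arms, and the protocol itself names transient neurological deficits as seen after it. A mild or moderate deficit of that kind is reportable if the child is in Arm A and not required if the child is in Arm B. The by-arm toxicity summary could then show low-grade MLA effects in one arm only, because of the reporting rule and not because of any difference between patients.

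Arm B is also the arm in which cytotoxic treatment follows the ablation within days. A complete record of procedure effects helps in reading whatever appears later. The blank 3-day cells add a little to this: the family attends for MRI and blood, but no exam or performance score is scheduled at that visit.

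What is at stake is the completeness of safety data from a pilot whose results are meant to inform later studies. No efficacy conclusion depends on it.

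**Working it through.** There is no planned figure to reproduce. The check sets the two arms side by side and derives the timing.

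| Item | Arm A | Arm B | Source |
|---|---|---|---|
| Lowest grade that must be reported, MLA-related event | 1 | 3 | 7.7 |
| Attribution needed | at least possibly MLA-related | none | 7.7 |
| Tracking window | 30 days after MLA | to 30 days after last treatment | 7.7 |
| Adverse event assessment starts | MLA day | MLA day | 10.1, 10.2 |
| Grade limit on Adverse Events Form | none stated | none stated | 11.0 |
| Exam and Karnofsky/Lansky at 3 days | both | neither | 10.1, 10.2 |
| Patients | 6 | 6 | 5.1.1, 5.1.2 |

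**Reporting gap.** A grade 1-2 MLA-related event meets the Arm A rule and fails the Arm B rule. Required any-grade reporting is 30 days in Arm A and 0 days in Arm B. For grade 3 or worse, Arm B's rule is the wider one. With six undelayed weekly doses from day 7, the last dose falls on day 7 + 5 × 7 = 42. Tracking then runs to day 42 + 30 = 72 even if no etoposide is given.

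**Could another section close it?** Section 7.7 has related events followed to resolution, but that governs follow-up and leaves the reporting threshold unchanged. Sections 7.2 and 7.6 cover unanticipated problems. Aphasia and hemiparesis are already described in the protocol, so grade 1-2 cases would ordinarily not count as unexpected. Section 9.6 records performance status at each physician visit but does not create a 3-day one.

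**Exam gap.** Interval from the 3-day visit to the first scheduled exam = max(0, first doxorubicin day − visit day).

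| First doxorubicin | Visit on day 3 | Visit on day 4 (5.1.2 allows this for the MRI) |
|---|---|---|
| day 2 | 0 | 0 |
| day 7 | 4 | 3 |
| day 14 | 11 | 10 |

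Week 1 also carries a window of ±3 days. The protocol does not say whether this adds to the 2-14 day range.

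**Scheduled exams in the first 30 days.** Arm A has 2 (3 days; 2-4 weeks). For Arm B, assuming weekly dosing without delay:

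- start on day 2: days 2, 9, 16, 23, 30, so 5;
- start on day 7: days 7, 14, 21, 28, so 4;
- start on day 14: days 14, 21, 28, so 3.

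**Length of the added rule.** If any-grade reporting in Arm B stopped at the first doxorubicin dose, it would cover 2/30 = 7%, 7/30 = 23% or 14/30 = 47% of Arm A's window for starts on day 2, 7 or 14. A full 30 days is needed to match. The price is 30 − 7 = 23 days of overlap with chemotherapy at the nominal start.

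**The case against.** The strongest reply is that the two rules are a reasonable choice. Arm A's MLA is followed by standard care at the physician's discretion, so attribution-based reporting fits. Arm B adds protocol chemotherapy, for which a grade 3 cut-off irrespective of cause is sensible, and that rule is broader in attribution and duration. No objective concerns low-grade toxicity, and an any-grade rule would bring shared attribution once doxorubicin starts. All of this stands, and it is why the existing Arm B rule should be kept. It does not explain why Arm A's rule for the shared procedure is left out of Arm B.

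Some stronger readings are tempting, and the documents do not support them:

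- *Arm B has no early exam, or is watched less after MLA.* It is examined weekly from Week 1 and has at least 3 scheduled exams by day 30 if dosing is not delayed, against 2 in Arm A. Counting 2 × 6 = 12 missing assessments looks at one calendar column only.
- *Mild deficits in Arm B would go unseen.* Adverse event assessment runs from the MLA day, overt deficits would probably be noted, and the form does not exclude low grades. The text supports only that they need not be reported.
- *Deficits would resolve before the first exam.* Section 1.3.1 gives no timing, so this is possible but unsupported.
- *Objective 3 has no pre-chemotherapy value in Arm B.* A Week 1 score taken before the 5-30 minute infusion is one. The calendar does not state that order, so a clarification is enough. Section 14.0 plans only descriptive summaries of the score, and the QOL Form line in Section 11.0 has no 3-day entry for either arm.

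**Conclusion.** The point holds in limited form. Section 7.7 leaves grade 1-2 MLA-related events outside required reporting in Arm B while requiring them for 30 days in Arm A, and no other section restores the requirement. The calendar difference is secondary: two blank cells, with a gap of nominally 4 days (range 0 to 11) before weekly exams begin. There is no gap if doxorubicin starts by day 3.

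This assumes that the Week 1 exam falls on the first doxorubicin day. The number of events affected cannot be estimated, because the documents give no frequency, onset or duration. No comparison of toxicity between arms is planned, and PFS, 6PFS and OS are unaffected. This is a low-priority, cheap improvement in safety capture and not a flaw in any planned conclusion.

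**What to change.** **Main change, Section 7.7.** Add a sentence for Arm B: in the 30 days after MLA, events of any grade considered at least possibly related to the MLA are also reported; once doxorubicin has started, an event may be attributed to both. Keep the present grade 3 rule and its window.

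**Secondary change, Section 10.2.** Mark physical exam (weight not needed, as in Arm A) and Karnofsky/Lansky in the 3-day column, done before the dose if doxorubicin starts by then. Add a footnote that the Week 1 performance status is recorded before the doxorubicin dose.

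**Cost.** One sentence, two calendar marks and a short footnote; one brief exam in each of six patients at a visit already scheduled for MRI and blood. No extra blood is needed. A day-3 sodium is not proposed, since Section 1.3.1 says "Hyponatremia resolved spontaneously" and gives no onset or frequency. The downsides are some additional low-grade reporting, shared attribution during doxorubicin, and an Arm B toxicity summary that may look less favourable.
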